3.1.7 ECOG performance status  $\leq 1$  (see Appendix 1)

3.1.8 Prior palliative radiotherapy to non-CNS lesions must have been completed at least 2 weeks prior to treatment. Subjects with symptomatic tumor lesions at baseline that may require palliative radiotherapy within 4 weeks of first treatment are strongly encouraged to receive palliative radiotherapy prior to treatment.

3.1.9 Patients must have normal organ and marrow function as defined below:

- WBC	$\geq 1,500/\text{mcL}$
- absolute neutrophil count	$\geq 1,000/\text{mcL}$
- hemoglobin	$\geq 8.0 \text{ g/dL}$
- platelets	$\geq 75,000/\text{mcL}$
- total bilirubin	$\leq 1.5 \times \text{institutional ULN}$ (patients with Gilbert's syndrome may have serum bilirubin $\leq 3 \times \text{ULN}$ )
- AST/ALT	$\leq 3 \times \text{institutional ULN}$ ( $\leq 5 \times \text{ULN}$ in the presence of liver metastases)
- creatinine	$\leq 1.5 \times \text{institutional ULN}$ or creatinine clearance (CrCl) $\geq 40 \text{ mL/min}$ (if using the Cockcroft-Gault formula below):

*Female:*

$$\text{CrCl} = \frac{(140 - \text{age in years}) \times \text{weight in kg} \times 0.85}{72 \times \text{serum creatinine in mg/dL}}$$

*Male:*

$$\text{CrCl} = \frac{(140 - \text{age in years}) \times \text{weight in kg} \times 1.00}{72 \times \text{serum creatinine in mg/dL}}$$

3.1.10 Age  $\geq 18$  years of age

3.1.11 Patients must have recovered from adverse events due to prior treatment to  $\leq$  grade 1, except for alopecia and sensory neuropathy  $\leq$  grade 2.

3.1.12 Patients must be able to understand and the willingness to sign a written informed consent document.

## 3.2 Exclusion Criteria

3.2.1 Subjects with poorly differentiated or small cell carcinoma histology

3.2.2 Subjects with disease that is amenable to surgical resection.

3.2.3 Subjects with history of or active symptoms of carcinoid or hormonal syndromes are permitted if symptoms are controlled with a somatostatin analog.

3.2.4 Hepatic intra-arterial embolization or peptide receptor radionuclide therapy (PRRT) within 4-8 weeks; cryoablation, radiofrequency ablation or trans-arterial chemoembolization of hepatic metastases within  $\leq$  4 weeks of study enrollment

3.2.5 Subjects with symptomatic untreated CNS metastases are excluded.

3.2.5.1 Subjects are eligible if CNS metastases are asymptomatic or adequately treated and subjects are neurologically returned to baseline (except for residual signs or symptoms related to the CNS treatment) for at least 2 weeks prior to first treatment.

3.2.5.2 In addition, subjects must be either off corticosteroids, or on a stable or decreasing dose of  $\leq$ 10 mg daily prednisone (or equivalent) for at least 2 weeks prior to first treatment.

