## **1. OBJECTIVES**

### **1.1 Primary Objective**

- 1.1.1 To determine the objective response rate (ORR) of advanced, progressive, well-differentiated nonfunctional NET of the lung, pancreas or gastrointestinal (GI) tract treated with nivolumab plus ipilimumab.

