### **1.2 Secondary Objectives**

- 1.2.1 To assess safety and tolerability of nivolumab plus ipilimumab by quantification of treatment dose interruptions and characterization of toxicities of the combination of nivolumab and ipilimumab in subjects with advanced well-differentiated nonfunctional NET of the lung, pancreas or GI tract.
- 1.2.2 To assess efficacy via progression free survival (PFS) at 6 months, 12 and 24 months of the combination of nivolumab and ipilimumab in subjects with advanced well-differentiated nonfunctional NET of the lung, pancreas or GI tract.
- 1.2.3 To further assess efficacy via median PFS, disease control rate (DCR), duration of response (DOR) and overall survival (OS) of the combination of nivolumab and ipilimumab in subjects with advanced well-differentiated nonfunctional NET of the lung, pancreas or GI tract.

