## STUDY SCHEMA

**Advanced or metastatic non-functional, well differentiated thoracic, GI or pancreatic NET  
No prior PD-1/PD-L1/CTLA-4 therapy  
ECOG PS 0-1**

**Nivo 240 mg Q2wks + Ipi 1mg/kg Q6wks  
Enrollment by tumor site of origin**

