## 2.4 Study Rationale

Subjects with progressive, non-functional advanced or metastatic thoracic, GI or pancreatic well-differentiated NETs are have few treatment options. The only FDA approved treatment regimen offers little response potential. In currently unpublished data with inhibitory immune checkpoint agents, patients with NET have shown promising clinical benefit. This therapy offers a novel approach to potentially provide long term benefit, but must be further explored.

The safety profile of nivolumab plus ipilimumab is characterized by immune-related toxicities, such as diarrhea, rash, pneumonitis, liver toxicity, and endocrinopathies (Nivolumab, Ipilimumab Investigator's Brochures). The frequencies and intensities of these events in the combination are variable and depend on the specific doses and schedule used. In the dosing schedules selected, these events were mostly low grade and manageable with the use of corticosteroids. Nivolumab and ipilimumab combination therapy has shown improved efficacy over either agent alone in melanoma.

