### **3. PATIENT SELECTION**

#### **3.1 Eligibility Criteria**

- 3.1.1 Subjects with histologically confirmed advanced, progressive, well-differentiated nonfunctional NET of the pancreas, lung or gastrointestinal (GI) tract per the 8th International Association for the Study of Lung Cancer classification (IASLC) or the American Joint Committee on Cancer (AJCC) Staging Handbook, 7th edition. Progression must be documented over the prior 12 months.
- 3.1.2 Measurable disease by CT or MRI per RECIST 1.1 criteria (Appendix 3); radiographic tumor assessment performed within 28 days before treatment. Target lesions may be located in a previously irradiated field if there is documented (radiographic) disease progression in that site after the completion of radiation therapy.
- 3.1.3 Prior therapy, including everolimus, octreotide, surgery, chemoradiation, is all permitted after being properly noted. This prior therapy must have been completed at least 28 days prior to study enrollment.
- 3.1.4 Patients with lung NETs must have progressed after at least 1 line of therapy. Patients with GI NETs must have had at least 2 lines of prior therapy.
- 3.1.5 Subjects are to have tumor tissue sample available at central lab for PD -L1 IHC testing during the screening period. Subjects can initiate therapy before the result of IHC testing.
- 3.1.6 (Stage 2 only) Subjects must be willing to undergo 2 sets of core needle biopsies (pre-treatment and at 6-8 weeks on therapy) if there are lesions amenable to biopsy. Subjects without a lesion amendable to biopsy will still be permitted to enroll provided they have an archival tumor sample for PD-L1 IHC testing. An optional core biopsy will be requested at progression.

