### 4.2 General Concomitant Medication and Supportive Care Guidelines

#### 4.2.1 Prohibited and/or Restricted Treatments

- 4.2.1.1 Systemic immunosuppressive agents are prohibited during the study, unless they are utilized to treat an adverse event. Allopurinol to prevent gout flares is allowed.
- 4.2.1.2 Concurrent administration of any anti-cancer therapies (investigational or approved) is also prohibited with the exception of subjects in the survival period of the study. This includes somatostatin analogues.
- 4.2.1.3 Any medicinal herbal preparation unless prescribed by the treating physician. All concomitant medications including prescribed medicinal herbal preparations must be documented.
- 4.2.1.4 G-CSF (granulocyte-colony stimulating factor) will be permitted. However, the use of these agents is allowed as per their respective label indications/institutional guidelines to treat neutropenia that occurs on study. G-CSF must not be used for the treatment of cancer or for any primary prophylaxis while on study.
- 4.2.1.5 Any non-oncology live viral vaccine therapies used for the prevention of infectious diseases within 12 weeks prior to study drug is prohibited. The use of the inactivated seasonal influenza vaccine will be permitted on study without restriction.

4.2.1.6 Alcohol consumption while on study is strongly discouraged due to the potential to confound interpretation of hepatotoxic events.

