4.2.1.7 Routine use of acetaminophen use is strongly discouraged

#### 4.2.2 Permitted Therapy

4.2.2.1 Regular concomitant use of bisphosphonates and RANK-L inhibitors for prevention or reduction of skeletal-related events in patients with bone metastases is allowed if initiated prior to first dose of study therapy.

4.2.2.2 Subjects are permitted the use of anti-emetic medications (with the exception of dexamethasone and/or other systemically administered steroids) at the treating physician's discretion.

4.2.2.3 Subjects are permitted the use of full-dose anti-coagulation (i.e. warfarin, enoxaparin, rivaroxaban, etc.) at the treating physician's discretion.

4.2.2.4 Subjects are permitted the use of topical, ocular, intra-articular, intranasal, and inhalational corticosteroids (with minimal systemic absorption).

4.2.2.5 Adrenal replacement steroid doses  $\leq$  10 mg daily prednisone are permitted.

4.2.2.6 A brief (less than 2 weeks) course of corticosteroids for prophylaxis (e.g., contrast dye allergy) or for treatment of non-autoimmune conditions (e.g., delayed-type hypersensitivity reaction caused by a contact allergen) is permitted.

4.2.2.7 Palliative local therapy, including palliative radiation therapy- and palliative surgical resection, is permitted prior to discontinuation of study treatment for subjects who do not have evidence of overall clinical or radiographic progression per RECIST 1.1.

Subjects requiring palliative local therapy should be evaluated for objective evidence of disease progression prior to the initiation of such therapy, particularly if the most recent tumor assessment was more than 4 weeks prior to the start of local therapy. If progression per RECISTv1.1 is identified on any tumor assessments prior to the initiation of palliative local therapy, then subjects must either discontinue study drug treatment or they must meet criteria to continue treatment beyond progression (**Section 5.3**) in order to resume immunotherapy after palliative local therapy.

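### Section 3.2.3 permits subjects whose active carcinoid or hormonal symptoms are controlled on a somatostatin analogue, but 4.2.1.2 bans the analogue on treatment and 3.1.1 requires nonfunctional NET

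*Combined protocol and SAP*

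**What the plan says.** All references are to the combined protocol and SAP.

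- **Entry (3.2.3).** Although it sits under Exclusion Criteria, the item is worded as a permission: "Subjects with history of or active symptoms of carcinoid or hormonal syndromes are permitted if symptoms are controlled with a somatostatin analog".
- **On treatment (4.2.1.2).** Concurrent anti-cancer therapy "is also prohibited with the exception of subjects in the survival period of the study. This includes somatostatin analogues".
- **Permitted therapy (4.2.2.1 to 4.2.2.7).** The list covers bone-protective agents, anti-emetics ("Subjects are permitted the use of anti-emetic medications"), anticoagulants, three kinds of corticosteroid use and palliative local therapy. It does not mention a somatostatin analogue.
- **Population.** 3.1.1 requires "Subjects with histologically confirmed advanced, progressive, well-differentiated nonfunctional NET of the pancreas, lung or gastrointestinal (GI) tract". The primary objective in 1.1.1 concerns "advanced, progressive, well-differentiated nonfunctional NET of the lung, pancreas or gastrointestinal (GI) tract treated with nivolumab plus ipilimumab". The secondary objectives ("in subjects with advanced well-differentiated nonfunctional NET of the lung, pancreas or GI tract"), the schema ("Advanced or metastatic non-functional, well differentiated thoracic, GI or pancreatic NET"), the rationale in 2.4 ("Subjects with progressive, non-functional advanced or metastatic thoracic, GI or pancreatic well-differentiated NETs") and 12.1 say the same in substance. The population sentence in 1.4 and the objective sentence in 2.4.1 leave the word out.
- **Meaning of functional (2.1).** The background ties carcinoid syndrome to functional tumors and contrasts these with nonfunctional ones. It says that an analogue often manages the symptoms, and separately that these drugs delay progression in advanced GI NET.
- **Washout (3.1.3).** Prior therapy, with octreotide among the examples, must have ended at least 28 days before enrollment.

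**The concern.** The drug that qualifies a subject under one rule is the drug that another rule forbids. A site with a patient whose flushing or diarrhea is held in check by an analogue finds that 3.2.3 allows entry because of that control, and that 4.2.1.2 then calls for the drug to be withdrawn. Stopping it risks the return of symptoms; continuing it is a protocol deviation. Different sites could settle this in different ways.

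The same patient also sits badly with the trial population. If active carcinoid syndrome marks a functional tumor, 3.2.3 permits on its face what 3.1.1 rules out. What is at stake is consistent enrollment, the safety of subjects who depend on the drug, and a clear description of whom the trial studied.

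**Working it through.** The plan gives no figure on this point, so the check sets the rules side by side.

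**Step 1: follow three kinds of subject through the rules.**

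| Subject | 3.2.3 | 3.1.1 | 3.1.3 | 4.2.1.2 |
|---|---|---|---|---|
| A. Active syndrome, controlled on an analogue | Permitted | Not met, if the contrast in 2.1 defines functional | Not met, if ongoing symptom treatment counts as prior therapy | Must stop the drug |
| B. History of a syndrome, no current need for an analogue | Permission fits poorly, as there are no current symptoms to control | Not settled by the text | No conflict | No conflict |
| C. No syndrome, analogue given for tumor control only | Not relevant | Met | Stop 28 days before enrollment | Drug stays off |

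Row C is coherent: washout and ban agree. Row B raises no drug conflict. The contradiction is confined to row A, where 3.2.3 says yes and each of the other three rules says no or probably no. The 3.1.3 entry is secondary, because the item does not say whether continuing symptom treatment is prior therapy.

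**Step 2: look for an exception that would rescue row A.** There are seven items in 4.2.2 (4.2.2.1 to 4.2.2.7), and 0 of 7 cover an analogue. The one exception inside 4.2.1.2 is the survival period, which comes after study treatment.

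**Step 3: ask whether the ban is limited by purpose.** It is not limited in words. Nearby items show that the protocol states such limits where it wants them. 4.2.1.1 excepts immunosuppressants given for an adverse event and allows allopurinol against gout flares. 4.2.1.4 allows G-CSF for neutropenia but not as cancer treatment or primary prophylaxis. 4.2.1.2 has no comparable clause for symptom control.

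**Step 4: count the population statements.** Nonfunctional describes the trial population in 1.1.1, 1.2.1, 1.2.2, 1.2.3, the schema, 2.4, 3.1.1 and 12.1: 1 + 3 + 1 + 1 + 1 + 1 = 8 places. 3.2.3 is the outlier.

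**Step 5: follow the consequence into the analysis rules.** 12.3.1 stops the best-overall-response window when subsequent anti-cancer therapy begins, and 12.3.2 censors PFS at the last evaluable assessment before it. Since 4.2.1.2 groups analogues with anti-cancer therapy, the text leaves open whether restarting one for symptoms would trigger either rule. No effect can be computed, because the documents give no number of such subjects.

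**The case against.** Four points deserve weight.

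*Criteria are cumulative.* Being permitted under 3.2.3 means only that a subject is not excluded on that ground; it does not waive 3.1.1. This stands. A reader might infer that 3.2.3 by itself brings functional tumors into the trial, but a site applying every criterion would stop at 3.1.1. What remains is that 3.2.3 and 3.1.1 give different answers for active syndromes, and that 3.2.3 has little purpose if 3.1.1 always prevails.

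*The ban can be read more softly.* Because 2.1 separates symptom control from delay of progression, a site could take 4.2.1.2 to mean antitumor use only. Or the sentence naming analogues could attach to the survival-period exception just before it. Neither reading is impossible. Neither states that an analogue may be continued during treatment, and the second still implies that analogues are otherwise covered by the ban. Two readings of a rule about a symptom-controlling drug are themselves a reason to clarify it.

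*Functional is never defined for eligibility.* True: 2.1 is background. The population conflict rests on its contrast, whereas the drug conflict does not need it.

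*The investigator has discretion.* 3.2.15 allows exclusion of a subject whose condition raises the risk. That limits harm case by case but does not say which rule governs.

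A reader might also infer that the response rate is biased or that the 5% null is wrong. The documents support neither. They give no response rate for functional NET and no expected number of affected subjects. The share of about 25% functional in 2.1 describes NET in general. The everolimus rates in 2.4.1 are 2% for nonfunctional lung and GI NET and 5% for pancreatic NET, and the latter is not labelled nonfunctional, so the null is not tied to nonfunctional disease alone.

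**Conclusion.** Wrong as written: an internal contradiction between one entry criterion (3.2.3) and the on-treatment ban (4.2.1.2), the nonfunctional requirement (3.1.1, with 1.1.1 and 12.1) and possibly the washout (3.1.3). Its reach is limited to subjects with active symptoms controlled on an analogue, whose number is unknown. It should be fixed because it concerns a drug that controls symptoms, and because correcting the wording is cheap.

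The conclusion assumes the plain reading of 4.2.1.2 and, for the population part, that the contrast in 2.1 is what nonfunctional means in 3.1.1. It does not extend to the primary analysis: the two-stage numbers in 12.2 (20, then 56 subjects) are not in question here.

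**What to change.** **Simplest route: reword 3.2.3.** Make it a true exclusion, for example: *Active carcinoid or hormonal syndrome, or a current need for a somatostatin analogue to control symptoms. A history of such a syndrome, with no current need for an analogue, is allowed.* This brings the outlier into line with 3.1.1, 3.1.3 and 4.2.1.2. It is one edit, with no added subjects, procedures or data items. The downside is narrower eligibility, by an amount that the documents do not allow one to estimate.

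**If the sponsor intends to admit controlled subjects,** the following need to change together:

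- 4.2.1.2 and 3.1.3: add an exception for a stable-dose analogue started before enrollment for symptom control (2 edits).
- 12.3.1 and 12.3.2: state that this use does not count as subsequent anti-cancer therapy for best overall response or PFS censoring (2 edits).
- The nonfunctional wording: align all 8 places.

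That is 2 + 2 + 8 = 12 edits, and it widens the target population. The choice belongs to the sponsor, because the text does not show which intent lay behind 3.2.3.

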3.2.6 Subjects with carcinomatous meningitis

3.2.7 Subjects must have recovered from the effects of major surgery or significant traumatic injury at least 14 days before first treatment.

3.2.8 Pregnant or breast-feeding women

3.2.9 Women of child-bearing potential, who are biologically able to conceive, and not employing two forms of highly effective contraception. Highly effective contraception must be used throughout the trial and up to 8 weeks after the last dose of study drug (e.g. male condom with spermicidal; diaphragm with spermicide; intra-uterine device). Women of child-bearing potential, defined as sexually mature women who have not undergone a hysterectomy or who have not been naturally postmenopausal for at least 12 consecutive months (i.e., who has had menses any time in the preceding 12 consecutive months), must have a negative serum pregnancy test  $\leq$  14 days prior to starting study drug.

3.2.10 Subjects with an active, known or suspected autoimmune disease. Subjects with type I diabetes mellitus, hypothyroidism only requiring hormone replacement, skin disorders (such as vitiligo, psoriasis, or alopecia) not requiring systemic treatment, or conditions not expected to recur in the absence of an external trigger are permitted to enroll.

3.2.11 Other active malignancy requiring concurrent intervention.

3.2.12 Subjects with a condition requiring systemic treatment with either corticosteroids ( $>$  10 mg daily prednisone equivalent) or other immunosuppressive medications within 14 days of first treatment. Inhaled or topical steroids, and adrenal replacement steroid 10 mg daily prednisone equivalent, are permitted in the absence of active autoimmune disease.

3.2.13 Subjects with interstitial lung disease that is symptomatic or may interfere with the detection or management of suspected drug-related pulmonary toxicity.

- 3.2.14 Known history of testing positive for human immunodeficiency virus (HIV) or known acquired immunodeficiency syndrome (AIDS).
- 3.2.15 Known medical condition that, in the investigator's opinion, would increase the risk associated with study participation or study drug administration or interferes with the interpretation of safety results.
- 3.2.16 Prior treatment with an anti-PD-1, anti-PD-L1, anti-PD-L2, anti-CTLA-4 antibody, or any other antibody or drug specifically targeting T-cell co-stimulation or checkpoint pathways
- 3.2.17 Any positive test for hepatitis B virus or hepatitis C virus indicating acute or chronic infection
- 3.2.18 History of allergy or hypersensitivity to study drug components

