## 6.1 Definitions

### 6.1.1 Adverse Event

An adverse event (AE) is defined as any new untoward medical occurrence or worsening of a preexisting medical condition in a clinical investigation subject administered study drug and that does not necessarily have a causal relationship with this treatment. An AE can therefore be any unfavorable and unintended sign (such as an abnormal laboratory finding), symptom, or disease temporally associated with the use of study drug, whether or not considered related to the study drug.

BMS will be reporting adverse events to regulatory authorities and ethics committees according to local applicable laws including European Directive 2001/20/EC and FDA Code of Federal Regulations 21 CFR Parts 312 and 320.

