### 6.6 Adverse Events of Interest

#### 6.6.1 Definition of immune-mediated adverse events (IMAEs)

Immune-mediated AEs are specific events (that include pneumonitis, diarrhea/colitis, hepatitis, nephritis/renal dysfunction, rash, and endocrine (adrenal insufficiency, hypothyroidism/thyroiditis, hyperthyroidism, diabetes mellitus, and hypophysitis) for which subjects received immunosuppressive medication for treatment of the event, with the exception of endocrine events (hypothyroidism/thyroiditis, hyperthyroidism, hypophysitis, diabetes mellitus, adrenal insufficiency), which are included regardless of treatment since these events are often managed without immunosuppression.

IMAEs include events, regardless of causality, occurring within 100 days of the last dose.

**Table 2** below provides a summary of the IMAEs category and their respective Preferred Terms (PTs).

Table 2: Preferred Terms Included in Analysis of IMAEs to Support Warnings and Precautions	
IMAE Category	Preferred Terms included under IMAE Category
Pneumonitis	Pneumonitis, Interstitial lung disease
Diarrhea/Colitis	Diarrhea, Colitis, Enterocolitis

**Table 2:** Preferred Terms Included in Analysis of IMAEs to Support Warnings and Precautions

IMAE Category	Preferred Terms included under IMAE Category
Hepatitis	Hepatotoxicity, Hepatitis, Hepatitis acute, Autoimmune Hepatitis, AST increased, ALT increased, Bilirubin increased, ALP increased
Adrenal insufficiency	Adrenal Insufficiency
Hypothyroidism/Thyroiditis	Hypothyroidism, Thyroiditis, Thyroiditis acute (collapsed with thyroiditis for frequency), Autoimmune thyroiditis (collapsed with thyroiditis for frequency)
Hyperthyroidism	Hyperthyroidism
Hypophysitis	Hypophysitis
Diabetes mellitus	Diabetes mellitus, Diabetic Ketoacidosis
Nephritis and renal dysfunction	Nephritis, Nephritis allergic, Tubulointerstitial nephritis

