#### 12.4.3 Safety Analyses

Safety analysis will be performed in all treated subjects. Descriptive statistics of safety will be presented using National Cancer Institute (NCI) Common Terminology Criteria for Adverse Events (CTCAE) version 4.0. All on-study AEs, drug-related AEs, SAEs and drug-related SAEs, AEs and drug-related AEs leading to drug discontinuation will be tabulated using worst grade per NCI CTCAE v 4.0 criteria by system organ class and preferred term, based on MedDRA terminology. On-study lab parameters including hematology, coagulation, chemistry, liver function and renal function will be summarized using worst grade per NCI CTCAE v 4.0 criteria.

Frequency, management and resolution of IMAEs will be analyzed. A tabular summary of the incidence of overall IMAEs (by preferred term) and serious IMAEs will be performed. A descriptive analysis of IMAEs including time-to-onset, severity, duration, action taken with the study drug, dosing delays of the study drug, corticosteroid details, re-challenge information and outcome of the AE will be individually characterized by IMAE category ([Section 6.6.1](#)).

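### Endocrine IMAE tables pool worsening of endocrine disease present at entry with new-onset events, over a denominator that includes subjects who already have the condition

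*Combined protocol and SAP*

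**What the plan says.** **Entry.** The exclusion criteria permit certain endocrine conditions by name. Section 3.2.10 admits "Subjects with type I diabetes mellitus, hypothyroidism only requiring hormone replacement", among others. Section 3.2.12 says inhaled or topical steroids and "adrenal replacement steroid 10 mg daily prednisone equivalent, are permitted in the absence of active autoimmune disease". Neither section limits how many such subjects may enter.

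**What becomes an adverse event.** Section 6.1.1 defines an adverse event as "any new untoward medical occurrence or worsening of a preexisting medical condition in a clinical investigation subject administered study drug". The opening of Section 6 starts collection at the first nivolumab dose and treats laboratory abnormalities found at screening as pre-treatment findings.

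**What becomes an IMAE.** Under Section 6.6.1 a non-endocrine event qualifies only if immunosuppressive medication was given for it. Endocrine events are exempt: they are events "which are included regardless of treatment since these events are often managed without immunosuppression". The section adds that "IMAEs include events, regardless of causality, occurring within 100 days of the last dose". Table 2 places diabetic ketoacidosis in the diabetes category and does not require new onset.

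**How it is reported.** Section 12.4.3 states "Safety analysis will be performed in all treated subjects" and "A tabular summary of the incidence of overall IMAEs (by preferred term) and serious IMAEs will be performed". It also describes time to onset, severity, duration, action taken, corticosteroid details, re-challenge and outcome by IMAE category. Neither baseline status nor causality is on that list.

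**The concern.** The conditions admitted at entry are also IMAE categories, and for those categories neither the treatment requirement nor causality limits what is counted. A subject with known type I diabetes who has a ketoacidosis for any reason enters the diabetes category beside a subject whose diabetes first appeared on treatment. A subject who already has a condition cannot develop it anew, yet remains in the denominator.

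Characterising toxicity is secondary objective 1.2.1. The trial has one arm, so no comparison removes the background rate of worsening. With at most 56 treated subjects planned, and 20 if the trial stops after stage 1, a few events move an endocrine rate. Table 2 is headed as supporting warnings and precautions, so readers are likely to take these figures as drug risk.

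**Working it through.** **The plan's own figures.** The documents state no prevalence of endocrine disease at entry and no expected endocrine IMAE rate, so there is no endocrine figure to reproduce. The only design figure used here is the number treated. The two-stage design in Section 12.2 (stop at 1 or fewer responses in 20; reject at 4 or fewer in 56) reproduces as stated: probability of early termination 0.736, expected size 20 + (1 − 0.7358) × 36 = 29.51, type I error 0.097, type II error 0.199. So N = 56, or 20 after an early stop.

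**Inputs.**
- N = 56 (Section 12.2).
- k = subjects with the condition at entry. Assumed 3, 6 or 9.
- i = new-onset risk among the other N − k. Assumed 15%, with 10% and 20% as alternatives.
- w = fraction of the k subjects with a recorded worsening. Assumed 0, 50% or 100%.

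**Formula.** Reported rate = [i × (N − k) + w × k] / N. This equals i + k × (w − i) / N, so the reported rate is below i when w < i, equal to it when w = i, and above it when w > i.

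**Worked case, k = 6, i = 15%.** Expected new-onset cases are 0.15 × 50 = 7.5.
- w = 0: 7.5 / 56 = 13.4%
- w = 50%: (7.5 + 3) / 56 = 18.8%
- w = 100%: (7.5 + 6) / 56 = 24.1%
- New onset among subjects at risk: 7.5 / 50 = 15%

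**Range over the assumptions (N = 56).**

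| i | k | w = 0 | w = 50% | w = 100% |
|---|---|---|---|---|
| 15% | 3 | 14.2% | 16.9% | 19.6% |
| 15% | 6 | 13.4% | 18.8% | 24.1% |
| 15% | 9 | 12.6% | 20.6% | 28.7% |
| 10% | 6 | 8.9% | 14.3% | 19.6% |
| 20% | 6 | 17.9% | 23.2% | 28.6% |

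The w = 100% column requires every affected subject to worsen and is an extreme bound. At k = 6, i = 15% and w = 10%, the reported rate is (7.5 + 0.6) / 56 = 14.5%, close to 15%.

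**Single-event case.** Suppose one subject is diabetic at entry and has one ketoacidosis, and no one else develops diabetes. The diabetes category shows 1/56 = 1.8% (exact 95% CI 0.05% to 9.6%). New onset among those at risk is 0/55 (exact 95% CI 0 to 6.5%). After a stop at 20, the same event shows as 1/20 = 5%.

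**Time to onset.** Worsening and new-onset dates enter one summary per category. The documents give nothing from which to size this effect.

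**The case against.** The strongest reply is that an IMAE must first be an adverse event. Section 6.1.1 requires a new occurrence or a worsening, and Section 6 starts collection at first dose and sets screening laboratory abnormalities aside. This stands. A reader might infer that background endocrine disease as such is tabulated as immune toxicity, with nothing to filter it out. The documents do not support that: stable disease cannot become an IMAE, and by itself it lowers the reported rate through the denominator.

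A reader might also infer that a routine change in thyroid replacement dose counts. That is not shown. A dose change is not in itself an untoward occurrence or a worsening, and the rule in Section 6 for grade 1 or 2 laboratory results is incomplete in the text available, so nothing here rests on it.

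Nor is the planned rate meaningless. It is the proportion of treated subjects with a new or worsened endocrine event of any cause up to 100 days after the last dose, and Section 6.6.1 gives a reason for the endocrine exemption. The planned rate does not, however, estimate new-onset toxicity.

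Section 12.4.3 also tabulates drug-related events separately, so a ketoacidosis judged unrelated would be absent there. The incidence table by preferred term shows ketoacidosis on its own line. Both help, but neither shows whether the subject was diabetic at entry. New and worsened hypothyroidism can share one preferred term. The drug-related tables are not the IMAE tables and use the same all-treated denominator. Section 3.2.15 allows exclusion of a condition that would interfere with interpreting safety, but at the investigator's discretion, whereas Section 3.2.10 permits these conditions by name.

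Finally, the shifts are small against sampling error: 8/56 has an exact 95% CI of 6.4% to 26.2%. That is fair, and it limits the weight of the point. The fault is nevertheless in the definition and can be removed by reporting.

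**Conclusion.** The point holds in a narrow form. Section 12.4.3 pools recorded worsening of admitted endocrine disease, of any cause, with new-onset events in both incidence and time to onset, and keeps subjects who already have the condition in the denominator. The effect is modest and its direction depends on how often existing disease worsens. In the central illustration the reported rate is 13.4% to 18.8% against 15% new onset among those at risk, with 24.1% as an extreme bound.

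The values of k, i and w are assumptions; only the 56 comes from the documents. The 15% is the new-onset risk and not the whole immune-mediated risk, because some worsening of existing disease could itself be immune-mediated. The safety analysis is descriptive and no test or stopping rule uses IMAE rates, so the response-rate analysis and the sample size are untouched. This is a worthwhile clarification of a secondary objective, not a defect in the trial's main conclusion.

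**What to change.** In Section 12.4.3, for each endocrine IMAE category:
- report incidence and time to onset of new-onset events among subjects without that condition in the screening history;
- list worsening of a pre-existing condition in a separate row, with the investigator's causality assessment;
- keep the all-treated count as Section 6.6.1 defines it.

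The study calendar in Section 9 already collects medical history, concurrent medication and thyroid tests at screening, so no new data are needed. It lists no adrenal function test at screening, so baseline adrenal status would rest on history and medication. Eligibility, treatment and follow-up do not change. The cost is a few lines of wording and one added table. The downside is that denominators differ slightly between endocrine categories, so each row should show its own.
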